5. ETHICAL REQUIREMENTS

5.1. Information to the subject

The purposes and modalities of the investigation will be explained to each subject through an information document (Informed Consent), containing what is verbally stated by the clinician. The subject will be required to date in his or her own hand and sign the consent document.

A copy of the document will be issued to the subject while the original will be kept by the investigator.

5.2. Usefulness of the results

There are currently no studies in the literature that have evaluated the efficacy of *Collagen Medical Devices* GUNA treatment in subjects with Achilles tendinopathy. The results of the present clinical investigation may provide useful elements for integrating therapeutic options in this patient population.

5.3. Adverse Events

An Adverse Event is defined as any harmful clinical event that will occur during the course of the clinical investigation in one of the subjects comprising the study population who has undergone one of the treatments in the investigation plan.

Adverse events will be classified into serious (SAE) non-serious (AE) and Suspected Serious and Unexpected Adverse Reactions (SUSAR).

An Adverse Event is defined as serious if (ICH-GCP DM 15/07/1997):

- it causes the death of the subject involved in the investigation
- places the subject's life in danger
- is such as to require hospitalization
- is such as to require prolonged hospitalization
- is such as to cause permanent or temporary disability
- leads to a congenital anomaly or birth defect

In all other cases, the Adverse Event will be non-serious and will be classified as:

- *mild* does not interfere with normal activities of daily living and resolves spontaneously;
- *moderate*, interferes with activities of daily living but resolves spontaneously;
- *severe*, prevents daily life activities and does not resolve spontaneously.

All personnel who come in contact with study subjects must report Adverse Events reported by subjects to the Investigator, who has a duty to collect all possible data about them.

- Adverse events (AEs) will be reported within 48 h by the Principal Investigator to the Clinical Research Unit of Guna S.p.a, through telephone, email, appropriate form and simultaneously through e-CRF.
- Serious Adverse Events (SAEs) and Suspected Serious and Unexpected Adverse Reactions (SUSARs) will have to be reported to the Sponsor immediately (within 24 h maximum) through telephone, email, appropriate form and simultaneously through e-CRF by the Principal Investigator and communicated to the Ethics Committee and the Ministry of Health.

The investigator should ensure that procedures are in place to ensure that the event is resolved.

In the case of nonserious Adverse Events (AEs), it is necessary to keep in mind that they can still give rise to serious events, which is why each Adverse Event must be monitored.

Adverse Events that have not yet resolved at the end of the study will be followed up by the Investigator; each subject who has experienced an Adverse Event will be contacted at least once a month after the conclusion of the study for as many months as deemed appropriate.

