3.14.1. Secondaries End Points

- Evaluation of VISA-A score at time T3w and T6w/FU compared to time T0
- Assessment of the VAS score at time T3w, T6w/FU and T8w/FU compared to time T0
- Evaluation of the SF12 questionnaire at time T3w, T6w/FU, and T8w/FU compared to time T0.
- Evaluation of the fraction of subjects in each group achieving Minimal Clinical Disease (MCD) considering that the MCD of the VISA-A questionnaire is 18.5 (90% MCD).
- Assessment of analgesic drug unit consumption based on clinical diary at time T3w, T6w/FU and time T8w/FU (paracetamol 1000 mg. will be used as "rescue dose" in case of onset/recurrence of pain).
- Evaluation of the fraction of subjects in each group who drop out early in relation to Adverse Events (AE/SAE/SUSAR).

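### The adverse-event severity scale ties intensity to spontaneous resolution, so three of six combinations have no grade

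*Protocol*

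**What the plan says.** Section 5.3 (Adverse Events) first lists the criteria that make an event serious. One of them is that the event "is such as to cause permanent or temporary disability". It then turns to everything else: "In all other cases, the Adverse Event will be non-serious and will be classified as" one of three grades:

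- mild: the event "does not interfere with normal activities of daily living and resolves spontaneously";
- moderate: it "interferes with activities of daily living but resolves spontaneously";
- severe: it "prevents daily life activities and does not resolve spontaneously".

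The section gives no residual category, no rule for an event that meets one half of a definition but not the other, and no definition of spontaneous resolution. The same section of the Combined protocol and SAP has the same wording, so neither document fills the gap left by the other.

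Three other statements in section 5.3 bear on the point. Non-serious events go to the sponsor within 48 h. Of the investigator it says: "The investigator should ensure that procedures are in place to ensure that the event is resolved". And events still open at the end of the study are to be followed up at least monthly.

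**The concern.** A severity scale should place every event it covers, and centres should place the same event in the same grade. This one asks two different questions in each definition. How much an event disturbs daily life is its intensity. Whether it clears without help is its outcome. The two need not move together: a minor event may need treatment or persist, and an event that stops normal activity may pass by itself. Where they part, the scale has no answer, although the section says that a grade will be given.

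At stake is the description of tolerability. The T1 and T2 visits (section 3.9.2) are defined as tolerability evaluations, and section 5.2 states that no earlier study has evaluated these collagen devices in Achilles tendinopathy. Readers will therefore look to this trial for a safety profile. If centres improvise for the ungraded events, severity counts cannot be compared between centres or reliably summarised by arm.

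**Working it through.** The plan states no figure on this point, so the check is an enumeration.

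**Inputs, all from section 5.3.** Intensity has three levels: does not interfere, interferes, prevents. Resolution has two states: spontaneous, not spontaneous. There are three grade definitions.

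**Step 1: cross the conditions.** 3 × 2 = 6 combinations.

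| Effect on daily activities | Resolves spontaneously | Does not resolve spontaneously |
|---|---|---|
| Does not interfere | mild | no grade |
| Interferes | moderate | no grade |
| Prevents | no grade | severe |

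Three cells are filled, and 6 − 3 = 3 are empty.

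**Step 2: how firm the count is.** It treats interfering and preventing as separate levels, as the definitions suggest. If preventing were read as an extreme form of interfering, the lower-left cell would become moderate and two cells would stay empty. That reading would put an activity-preventing event below severe only because it passed by itself.

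**Step 3: can the empty cells occur?** The right-hand column takes in any event that needed intervention to clear and any event that has not cleared. Section 5.3 foresees both: it asks for procedures to bring events to resolution, and it provides follow-up for events open at study end. A minor event still open then does not meet the definition of mild or moderate, and it does not meet severe because it does not prevent activities. The lower-left cell is narrower, because an event that causes even temporary disability is serious and leaves the scale. What remains is an event that prevents daily activities, passes by itself and is not judged a disability. The documents do not say where that line falls.

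**Step 4: timing.** Non-serious events are reported within 48 h. Section 5.3 does not say when the grade is assigned. If it is given with the report, half of each definition may still be unknown. A grade on intensity alone would not have that difficulty.

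**Step 5: how many centres must interpret the rule.** Section 3.8 caps each centre at 18 subjects, and 72 / 18 = 4, so at least four centres must grade events.

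**Step 6: where the grade is used.** The only adverse-event endpoint in section 3.14 is early dropout related to adverse events, which section 4.15 compares with Fisher's exact test. It does not use the grade. The 48 h and 24 h reporting limits depend on seriousness, not on severity.

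**The case against.** The strongest case on the other side is that the gap has little consequence. No endpoint, test, planned table or reporting deadline uses the severity grade. All events are still recorded, monitored and followed. An event that disables the subject, even temporarily, is already caught as serious. The eCRF and the reporting form are not among the documents, so outcome and treatment fields may already exist. All of this stands. It limits the size of the point, but it does not supply the missing grades.

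Three stronger readings are tempting, and the documents do not support them.

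- **Minor events are pushed into severe.** A reader might infer this because severe is the only grade that mentions non-spontaneous resolution. But severe also requires that daily activities are prevented. A minor event that does not clear by itself fails that definition too, so by the letter it is ungraded, not over-graded.
- **Pain treated with rescue paracetamol loses its grade.** Section 3.14 provides paracetamol "in case of onset/recurrence of pain", as part of an analgesic-consumption endpoint. It is not described there as treatment of adverse events. Section 5.3 does not say that taking an analgesic means an event did not resolve spontaneously, and neither document mentions injection-site pain.
- **The problem falls mainly on Group A.** Only that group is injected, at most 36 × 6 = 216 times. But injections are exposures, not events, and the documents give no adverse-event rate. Both groups do the twice-daily loaded exercises in section 3.12 and may use paracetamol, so events in Group B can fall into the same cells.

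**Conclusion.** The point holds as a defect of definition. Section 5.3 requires a grade for every non-serious event and provides one for three of the six combinations its own terms create. The count assumes that the three intensity levels are mutually exclusive, and the third gap applies only to events not already serious as temporary disability.

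The share of events affected cannot be estimated from the documents; three of six is a count of cells, not of events. The supported consequence is missing or inconsistent descriptive grading in either arm. A reader might go further and say that the device's severity profile will be wrong. The documents do not show that, and the efficacy analysis and the comparison of adverse-event dropout are untouched. It is a minor point, worth correcting because the rule cannot be followed as written and the repair is nearly free.

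**What to change.** In section 5.3 of both documents, define severity by intensity only, with the three levels the section already has: mild for events that do not interfere with daily activities, moderate for those that interfere, severe for those that prevent them. Remove spontaneous resolution from all three definitions. All six combinations then have a grade, and the grade can be given when the event is reported.

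So that nothing is lost, record the outcome of the event and any treatment given for it as separate eCRF items, after checking whether those items exist already.

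The cost is a wording edit in section 5.3 of each document and at most one or two eCRF fields. No visit, endpoint, test or sample size changes.

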5.4. Privacy Protection

The identities of data subjects will be known only to the Investigators and the Clinical Monitor in charge of monitoring the investigation. Reference will be made to Regulation (EU) 2017/745.

5.5. Data properties

All data collected will belong to Guna S.p.a. Milan, Italy, sponsor of the clinical study. Additional information regarding data ownership can be found in the Economic Agreement document.

5.6. Data processing and publication

Full respect for the anonymity of the subjects participating in the clinical study will be ensured. Data collection, data processing, any scientific publications or presentations at conferences of the results of the clinical study will be conducted in accordance with the Current Privacy Legislation. Regulation (EU) 2017/745

5.7. Funding

This research is funded by GUNA S.p.a.
Please refer to the Economic Agreement for further information.

5.8. Reference Code of Ethics.

Reference is made to the Declaration of Helsinki (Fortaleza 64th 2013) and the principles of Good Clinical Practice (GCP) will be followed (D.leg. June 24, 2003 - n.211 at G.U. n.184 of 09/08/2003).

5.9. Subjects Insurance

Insurance coverage for all enrolled subjects will be provided by GUNA S.p.a for the entire duration of the clinical study project.

6. PREMATURE TERMINATION OF THE CLINICAL INVESTIGATION

The Investigators reserve the right to discontinue the investigation at any time for reasonable medical and/or administrative reasons. Reasons for discontinuation will be documented; the Ethics Committee and the Ministry of Health will be informed of the decision.

7. GLOSSARY

Medical device: Any instrument, apparatus, implant, substance or other product, whether used alone or in combination, including computer software used for proper functioning, and intended by the manufacturer for use in man for the purpose of diagnosis prevention, control, therapy or mitigation of a disease; diagnosis, control, therapy, mitigation or compensation for an injury or handicap of study, replacement or modification of anatomy or a physiological process; of intervention in conception, which product does not exert its principal action, in or on the human body, for which it is intended, by pharmacological or immunological means, nor by metabolic process but whose function may be assisted by such means.

8. ATTACHMENTS TO THE INVESTIGATIONAL STUDY PLAN

- A.** Synopsis of the Investigation
- B.** Informed Consent (disclosure and consent)
- C.** Consent to the processing of personal data (information and consent)
- D.** VISA-A questionnaire
- E.** Pain Visual Analog Scale (VAS)
- F.** SF12 questionnaire
- G.** Clinical diary
- H.** Physiotherapy booklet
- I.** Flow chart of the investigation

## 2. INTRODUCTION

### 2.1 Insertional-non-insertional-mixed yarrow tendinopathy

Achilles tendinopathy is a condition characterized by inflammation of the Achilles tendon. The latter is the largest tendon in the human body, is about 15 cm long, and originates from the triceps muscle of the sura, formed by the twin muscles, whose tendon fibers insert postero-laterally to the calcaneal bone, and the soleus, whose tendon fibers insert antero-medially to the calcaneal bone, giving rise precisely to the Achilles tendon.

Two types of forces act on the Achilles tendon: one exerted by the tendons of the gastrocnemius and soleus muscles, and one resulting from the compressive action of the calcaneal bone on the tendon. In case of excessive mechanical stress by these two forces, the tendon undergoes degeneration triggering tendinopathy [1].

Approximately 6% of the general population suffers from achilles tendinopathy during their lifetime [2]. Achilles tendinopathies are classified into insertional tendinitis and noninsertional tendinitis. Insertional tendinitis involves the lower part of the tendon, where the tendon inserts at the level of the calcaneus, and can affect even patients who are not particularly athletically active [3].

Noninsertional tendinitis occurs when the fibers in the middle portion of the tendon are affected, affects young and athletic people the most and has a high incidence (30-50%) in middle-aged individuals. Such pathology in the young and athletic patient often requires a complete cessation of physical activities for long periods of time and may go so far as to interfere with work activities, thus in fact constituting a significant social cost, as well as a highly disabling and impacting factor on the patient's quality of life.

Clinically, patients present with reduced dorsiflexion and plantarflexion deficits with acupressure tenderness in the insertional and noninsertional sites of the affected achilles region. On inspection of the posterior calcaneal portion, patients may present with an erythematous and mildly edematous area associated with an initial picture of swelling at the achilles site. Patients also report pain aggravated by exercise (running, jumping, walking).

Regarding diagnosis, in the first instance, it is advisable to perform a standard loaded radiograph of the foot to visualize any enthesopathy and peri- and intra-tendinous calcifications. It is also advisable to perform a musculoskeletal ultrasonography and as a second-level investigation an MRI, in order to visualize optimally the soft tissues and thus a tendon degeneration, although signs of tendon degeneration are not always accompanied by a positive clinical picture, either in the acute or subacute phase.

We can distinguish conservative and nonconservative treatments.

Conservative treatments include: exercise in an eccentric regimen as recommended by the 2010 "American Physical Therapy Association" guidelines (Grade A) [4]; focused shock wave physical therapy as suggested by the recent study by "Chimenti et al. " of 2017 (Grade B) [1]; the use of nocturnal splints,

on the other hand, does not present sufficient evidence to justify their use; corticosteroid and platelet-rich plasma (PRP) infiltrations, although frequently used in clinical practice, are not supported by solid scientific evidence.

In the literature, by contrast, we recall the 2012 study by Monto RR. who reports the satisfaction of 28 out of 30 patients with achilles tendinopathy treated with PRP [5] and several other Authors who have gained experience in this regard [6;7;8;9;10;11]. The use of SVF adipose stromal fraction in the treatment of tendinopathies is still being studied [12;13].

Non-conservative treatments include various surgical approaches, which may involve more complex tendon transfer surgeries, such as transposition of the long flexor hallux, or simpler scarification approaches; minimally invasive endoscopic approaches; or percutaneous echo-guided procedures, all of which currently lack sufficient scientific support.

Conservative treatment alone is often found to be unsatisfactory in 40% of cases, while proposed traditional and minimally invasive surgical treatments (such as scarifications) have mixed results and are not always reproducible in the literature.

In light of this, there appears to be a clear need to find minimally invasive therapeutic alternatives that can guarantee to achieve better results than the current ones in the early treatment of acute and subacute insertional and noninsertional achilles tendinopathies.

## 2.2 Role of collagen in the pathogenesis of Achilles tendinopathy

Recently, a line of medical devices based on collagen and ancillary substances has been produced by Guna S.p.a., including MD-Tissue Collagen Medical Device. Collagen is the most abundant protein in mammals, accounting for about 5 to 6 % of an adult human's body weight. A third to a quarter of all protein mass in higher animals is collagen: from bones to tendons, joint capsules to muscles, ligaments to fasciae, teeth to serosae, and skin to extracellular matrix (ECM). It is found in most tissues, and particularly in those tissues that require both flexibility and strength such as skin, tendons, and muscle fascias. There are 14 types of collagen, the most represented type being type I. In humans, the peak of collagen biosynthesis occurs from age 45 to 60. Thereafter, its production drops very rapidly, along with that of elastin and proteoglycans. The unit-base of collagen is tropocollagen, a glycoprotein formed by the intertwining of three left-handed polypeptide chains carrying glucose and galactose molecules, attached only to the amino acid molecule Hydroxylysine (Hyl), one of only four amino acids constituting tropo-collagen with Glycine (Gly), Proline (Pro) and 4-Hydroxyproline (Hyp). This tight triple helix provides the structural strength and rigidity, but also the strength and flexibility necessary for perfect collagen function. The arrangement of fibrils in the formation of collagen fibers, provides the structure with great robustness in terms of strength, inextensibility, incompressibility, but also plasticity, flexibility, resistance to loading, and resistance to twisting. Due to its abundance in nature (more than 90 % of fibrous proteins are made up of type I collagen) and its unique physical and

biological properties, type I collagen has been used extensively to produce medical devices, and among these are the injectable medical devices produced by Guna S.p.a. called Collagen Medical Devices based on porcine collagen. In orthopedics and traumatology and in rehabilitation medicine, this evidence on the structural role of collagen holds particular importance since all extra- and intra-articular structures are basically made up of this molecule [14;15;16].

### 2.3. Collagen in the therapy of achilles tendinopathy

In view of the morpho-structural changes that characterize Achilles tendinopathy, the use of injectable medical devices such as Collagen Medical Devices might find therapeutic indication. For some years now, in fact, the use of injectable medical devices based on porcine collagen and ancillary substances of natural origin (*Collagen Medical Devices* GUNA) has been introduced in the treatment of painful and degenerative pathologies of the locomotor system, which allow a more effective and specific placement of collagen in situ with the function of vehiculation and stabilization. The collagen used in Collagen Medical Devices GUNA undergoes a special process of tangential filtration, sterilization, and molecular weight control, resulting in a pure product. Infiltrative therapy based on *Collagen Medical Devices* would make it possible to replace, reinforce, structure and protect (adhesion barrier) cartilage, tendons, ligaments, joint capsules, etc., improving the arrangement of collagen fibers and all the anatomical structures in which it is present and, at the same time, provide mechanical type support to the affected district.

In particular, MD-Tissue *Collagen Medical Device* could play a positive role in the treatment of Achilles tendon pathology.

## 3. SCIENTIFIC REQUIREMENTS

### 3.1. Title of the research

Evaluation of collagen-based medical device treatment combined with physiotherapy in subjects with achilles tendinopathy. Multicenter randomized clinical investigation; AKITENMED STUDY.

### 3.2. Purpose of research

Considering that there are no strong evidence-based guidelines in the area of treatment of achilles tendinopathy, the purpose of this research project is to understand through a multicenter, randomized clinical investigation the impact of treatment with a porcine collagen-based medical device administered in the peri-tendon area in combination with physiotherapy on pain reduction and functional improvement of the investigated tendon.

### 3.3. Design of the clinical investigation

The multicenter, randomized clinical investigation is prospective, and will have a total duration of 8 weeks.

After enrollment, subjects will be randomized and assigned to two experimental groups:

- **Group A** which, alongside physiotherapy (eccentric strengthening protocol) will receive MD-Tissue Collagen Medical Device.
- **Group B** which, will implement only physiotherapy (eccentric strengthening protocol).

Variables will be assessed at baseline (T0 time), after 1 week (T1w), after 2 weeks (T2w), after 3 weeks (T3w), or at the end of injection treatment, and after 6 weeks after enrollment (T6w/FU). Further evaluation will be carried out after 2 weeks, or after 8 weeks (T8w/FU) from the start of the clinical investigation.

After enrollment, subjects in both groups will begin a 6-week physiotherapy course (eccentric strengthening protocol). Each session will consist of Achilles tendon stretching exercises. See § 3.12.

